5.2. Study treatment and procedures

5.2.1. Screening and Enrollment

Patients with active UC that are part of the Boston Children's Hospital Gastroenterology and Nutrition clinic as well as referrals from outside of BCH will be pre-screened for study participation. Potential subjects who agree to participate in the study will have a medical exam with labs to assess eligibility. Participants will also undergo a baseline serologic assessment of HIV, HBV and HCV status within 2 weeks prior to the first FMT dose. Females who have achieved menses will undergo urine hCG testing. These four lab tests are considered for research purposes only.

It is expected that study participants will receive ongoing clinical care at BCH for the duration of the study. Study participants, who self-refer or are referred by a GI provider not at BCH, will have their primary GI provider notified of their participation in the FMT study and follow up clinical care at BCH during the course of the study at planned intervals. The study PI will provide the primary GI provider with contact information to relay any questions and concerns during the study period. At the completion of the subject's involvement in the study, the PI will provide a final written and/or verbal report to the primary GI provider for continuity of care.

Presence of active mucosal inflammatory bowel disease (active colitis) is an eligibility requirement for this study. Subjects with evidence of inflammation in a prior staging colonoscopy completed no more than 105 days will not be required to repeat a standard staging colonoscopy solely for the purposes of research. Subjects who have no evidence of active disease by endoscopic scoring of disease at the time of staging colonoscopy will not be randomized and will be excluded from the study.

An initial subset of 10 subjects will be limited to patients with mild to moderate Ulcerative colitis (i.e., PUCAI < 65) and to individuals ≥ 12 years of age.

Upon confirmation of eligibility and completion of randomization, subjects will receive an induction antibiotic regimen (or corresponding placebo if in placebo arm) for one week to decrease levels of indigenous microflora (Study Day -8 until Day -1).

The antibiotic regimen will include:

1) A double antibiotic capsule containing vancomycin 125 mg and polymixin 62.5 mg to be administered orally (PO) according to the following body surface area (BSA) parameters:

BSA* (m ²)	Capsule	Frequency				
< 0.5	1	3 times a day				
0.5-1	2	3 times a day				
1-1.5	3	3 times a day				
1.5-2	4	3 times a day				

*BSA will be calculated as **BSA = SQRT [(cm*kg)/3600]**

2) A third antibiotic metronidazole administered orally (PO) as a separate capsule according to the following weight-based dosing parameters:

Patient Wt (kg)	Dose (mg)	Frequency			
12.5 - 25.0	125	2 times a day			
25.0 - 37.5	250	2 times a day			
37.5 - 50.0	375	2 times a day			
>50.0	500	2 times a day			

Corresponding placebo for each antibiotic will be supplied and distributed by the BCH Research Pharmacy.

Clinical data including symptom logs, medications and disease activity and stool samples will be collected at the time of study entry and after completion of the antibiotic regimen. Routine laboratory analysis will be done at the time of enrollment and before commencing study treatment.

Subjects who meet all eligibility criteria will be randomized to receive either FMT or placebo.

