3.2.1. Inclusion Criteria

Male and female children and young adults, aged 5 years to 30 years, who meet the following inclusion criteria, will be enrolled in the study.

An initial subset of 10 subjects will be limited to patients with mild to moderate ulcerative colitis (i.e., PUCAI < 65) and to individuals ≥ 12 years of age. If FMT appears to be safe in this subset of patients after 8 weeks in the study (to be assessed by a Data Safety Monitoring Board), expanded enrollment as is described above will occur.

All patients must satisfy below criteria:

- 1. Have UC (PUCAI >9) and have failed, are intolerant to, or have refused first-line maintenance therapy.
- 2. Have had visual or histologic evidence of inflammation confirmed through colonoscopy ideally within 90 days but no more than 105 days prior to randomization.
- 3. Have negative test results for Hepatitis B (HBV), Hepatitis C (HCV), and Human Immunodeficiency Virus (HIV).
- 4. Have a negative urine hCG test if female of childbearing potential.
- 5. Able to swallow antibiotic, FMT or placebo capsules.
- 6. Able to give informed consent and/or assent as appropriate (patients 12-17 will be asked to provide written assent, patients 5-11 will be observed for assent or dissent behaviorally, or with verbal/written communication)
- 7. Willing and able to participate in the study requirements, including serial stool collection, survey completion and clinic visits.
- 8. Willing to undergo telephone follow-up to assess for safety and adverse events.
- 9. Must be free of any known food allergy.
- 10. Agrees and willing to have an enema for purposes of induction therapy.

Patients who have disease that has required other medications (including steroids, immunosuppressives, and biologics) will be included.

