3.2.2. Exclusion Criteria

Subjects who fall into any of the following exclusion criteria at the time of screening are not eligible for enrollment into the study.

- 1. Patients in a clinical remission (PUCAI \leq 9).
- 2. Patients with recent (within 4 weeks) dose change of biologics, 5-ASA, steroids or immunomodulators
- 3. Patients considered to have toxic megacolon.
- 4. Patients with a known drug allergy to vancomycin, metronidazole or polymyxin.
- 5. Patients with a history of aspiration, gastroparesis, surgery involving the upper gastrointestinal tract (that might affect upper gastrointestinal motility) or unable to swallow pills.
- 6. Patients with esophageal dysmotility or swallowing dysfunction.
- 7. Patients with known food allergies.
- 8. Patients with positive test results for HBV, HCV, or HIV.
- 9. Female patients with a positive test result on a urine hCG test.
- 10. Patients unwilling or unable to give consent or participate in all study requirements.
- 11. Patients unable or unwilling to receive a retention enema for purposes of induction therapy.

- 12. Patients with recent (within 6 weeks) systemic antibiotic use.
- 13. Patients who have testing consistent with active clostridium difficile.
- 14. Patients with known prior experience with donor FMT.

Research personnel and care providers will be educated about inclusion/exclusion criteria so that only appropriate patients are approached for informed consent. This will reduce the burden of worry for families and patients as to whether they are suitable candidates for the study. Subjects who are found to have no evidence of active disease by colonoscopy will be excluded from the study.

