7.3. Data Analysis

All patients who are eligible, randomized, and have received at least one-dose of the study medication including antibiotics/placebo in the first week will be included into the analysis for primary outcomes to assess the safety and tolerability of FMT, as this will be a per protocol (and not intent-to-treat) analysis . Continuous variables will be presented as mean and standard deviation (SD) or median and interquartile range (IQR), depending on the distribution of the data. Categorical variables will be presented as number and percentage. Disease severity (PUCAI) and patient characteristics at baseline will be compared between the treatment groups to determine whether or not randomization resulted in balanced groups. Methods of 2-group comparison will include Student's t-test, the Mann-Whitney test, Pearson chi-square test, and Fisher exact test, depending on the distribution of the variable under consideration. The primary outcome of safety will be assessed via a 2×2 cross-tabulation, where the proportion of patients with new incident SAEs or upgrade of existing AEs in the FMT group will be compared to the proportion in the placebo group. Two one-sided tests for equivalence (32) will be constructed and the overall *P* value taken to be the larger of the lower and upper tests. Statistical significance will be assessed at *P*<0.05.

For the second outcome, we will use longitudinal data analysis methods to investigate changes in inflammatory biomarkers including stool calprotectin, stool lactoferrin, serum ESR/CRP, albumin, and hematocrit over the study period. Generalized Estimating Equations will be performed to examine the association between FMT and changes in these biomarkers.

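### A subject with inflammation on histology only is admitted by 3.2.1 and barred by 5.2.1, and 7.3 makes eligibility a condition of the primary safety analysis

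*Combined protocol and SAP*

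**What the plan says.** **Section 3.2.1, Inclusion Criteria.** The list is introduced with "All patients must satisfy below criteria". Criterion 2 reads "Have had visual or histologic evidence of inflammation confirmed through colonoscopy", followed by a time window. Either kind of evidence is enough.

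**Section 3.2.2, Exclusion Criteria, closing sentence.** "Subjects who are found to have no evidence of active disease by colonoscopy will be excluded from the study". It does not say whether biopsy findings count.

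**Section 5.2.1, Screening and Enrollment.** The general requirement is "Presence of active mucosal inflammatory bowel disease (active colitis) is an eligibility requirement for this study", with no method named. The operative rule is narrower: subjects with "no evidence of active disease by endoscopic scoring of disease at the time of staging colonoscopy" are kept out of randomisation and excluded. It makes no exception for histology and names no score or cut-off. The section ends: "Subjects who meet all eligibility criteria will be randomized to receive either FMT or placebo".

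**Section 7.3, Data Analysis.** The primary safety analysis covers "All patients who are eligible, randomized, and have received at least one-dose" of study medication, antibiotics or their placebo included. The section labels this a per-protocol analysis, as distinct from intent-to-treat.

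**Section 5.2.3.** Each subject's assignment is unblinded after the last blinded dose at Week 8.

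**The concern.** Two rules in current text give opposite enrolment decisions for the same person. That alone needs correcting, because staff screening such a subject cannot comply with both.

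The statistical interest comes from 7.3. It lists eligibility as a condition separate from being randomised and dosed. If every randomised subject were eligible without dispute, the word would do nothing. Where the eligibility text contradicts itself, a randomised and dosed subject could later be classed either way. The plan does not say which definition governs the analysis set, when the decision is made, or that it is made blind. Since unblinding is subject by subject after Week 8, the decision could be taken with outcome and arm known. In a safety comparison planned on about three events per arm, the handling of one subject with an event could matter.

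**Working it through.** **Step 1. The eligibility text, applied to one subject.** Take a subject with PUCAI above 9, a staging colonoscopy inside the window, no active disease on endoscopic scoring, inflamed biopsies, and all other criteria met.

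| Source | Test applied | Result |
|---|---|---|
| 3.2.1 criterion 2 | visual or histologic | admitted |
| 3.2.2 closing sentence | by colonoscopy, biopsy not mentioned | undetermined |
| 5.2.1 general requirement | active mucosal disease, method not named | undetermined |
| 5.2.1 operative rule | endoscopic scoring | barred |

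Reading 5.2.1 strictly leaves the histologic alternative in criterion 2 without effect. Reading criterion 2 as written overrides 5.2.1.

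**Step 2. When the rules act.** The Schedule of Events (5.1) puts eligibility and colonoscopy at Day -90 to -9 and randomisation at Day -8. There are two branches.

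- 5.2.1 is enforced at screening: the subject is never randomised and the analysis set is untouched.
- The subject is randomised under 3.2.1 and dosed: 7.3 includes the subject only if classed as eligible, and the text supports either classification.

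**Step 3. What one removal does in the second branch.** The plan gives no figure on this point to reproduce. Inputs from 7.1 and 7.3: 30 per arm, a 10% placebo rate (0.10 × 30 = 3 events), a 0.20 margin paired with that rate, two one-sided tests with the larger P taken, and P < 0.05. The variance method is not stated; I assume Wald with unpooled variance.

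With d = p(FMT) − p(placebo):

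- SE = √[p_F(1−p_F)/n_F + p_P(1−p_P)/n_P]
- z = (0.20 − |d|)/SE, which is the smaller of the two test statistics
- P = 1 − Φ(z)
- 90% limits = d ± 1.645 × SE

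Placebo is held at 3/30, and one FMT subject with an event is removed:

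| FMT | d | SE | z | P | 90% limits, points | Equivalence |
|---|---|---|---|---|---|---|
| 3/30 | 0.0000 | 0.0775 | 2.582 | 0.005 | −12.7 to +12.7 | shown |
| 2/29 | −0.0310 | 0.0722 | 2.340 | 0.010 | −15.0 to +8.8 | shown |
| 4/30 | 0.0333 | 0.0828 | 2.013 | 0.022 | −10.3 to +17.0 | shown |
| 3/29 | 0.0034 | 0.0787 | 2.497 | 0.006 | −12.6 to +13.3 | shown |
| 5/30 | 0.0667 | 0.0873 | 1.526 | 0.063 | −7.7 to +21.0 | **not shown** |
| 4/29 | 0.0379 | 0.0843 | 1.923 | 0.027 | −10.1 to +17.7 | **shown** |
| 6/30 | 0.1000 | 0.0913 | 1.095 | 0.137 | −5.0 to +25.0 | not shown |
| 5/29 | 0.0724 | 0.0890 | 1.434 | 0.076 | −7.4 to +21.9 | not shown |

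Removal lowers both numerator and denominator, so the shift is 3/30 − 2/29 = 10.0 − 6.9 = 3.1 points in the first pair and 5/30 − 4/29 = 16.7 − 13.8 = 2.9 points in the third. Of the four pairs, only the one starting at 5/30 changes its conclusion.

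**Step 4. Dependence on the margin.** Section 7.1 also mentions 0.25, paired with a 15% rate. At 0.25, 5/30 against 3/30 gives z = (0.25 − 0.0667)/0.0873 = 2.10 and P = 0.018, so equivalence is shown before any removal and this example no longer changes.

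**The case against.** The strongest reply is that both rules act before randomisation. Section 5.2.1 says such subjects are not randomised, only those meeting all criteria proceed, and this is a single-center trial, so different sites cannot apply different passages. No section provides for eligibility to be reviewed again later. Section 3.2.3 allows withdrawal of a subject who does not meet the criteria, but withdrawal from participation is not removal from analysis. The only exclusion from the per-protocol analysis that is spelled out (3.2.4) concerns screen failures who never began conditioning. This stands: the effect on the analysis is conditional, and a reader who infers that the plan provides for exclusions made in knowledge of outcome goes beyond the text.

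A second reply is that an exclusion may properly narrow an inclusion, and that the softer sentences in 3.2.2 and 5.2.1 suggest loose drafting. That may explain the wording but does not reconcile it, because the endoscopic rule still cancels an alternative that criterion 2 expressly grants.

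A third reply is that *eligible* in 7.3 could remove a subject on any criterion, so it is a general analysis-set matter. That is correct. The endoscopy and histology conflict is one identifiable case in which the word has no settled meaning.

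Two further inferences are tempting and unsupported. One is that any single removal could decide the trial; the table shows it does so only near the margin. The other is that a particular number of subjects is affected; the documents give no share with histology-only disease, and those subjects must also have PUCAI above 9.

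**Conclusion.** The point holds as an internal contradiction with a conditional consequence for the primary analysis. The contradiction itself is certain from current text and rests on no assumption.

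The size depends on practice. With 5.2.1 enforced at screening, the consequence is inconsistent enrolment and an inclusion criterion that misstates who may enter. If a histology-only subject is randomised, 7.3 leaves a route to exclusion after randomisation. One removed FMT event shifts the difference by about 3 points, and it reverses the conclusion in the 5/30 against 3/30 case (P = 0.063 to 0.027). That example assumes Wald tests, a 0.20 margin and three placebo events; it is an illustration and not a forecast. The number of subjects at risk is unknown. The change should be made because it is cheap and closes the route entirely, not because bias has been shown.

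**What to change.** 1. Reconcile 3.2.1 criterion 2, the closing sentence of 3.2.2 and the operative rule in 5.2.1 to one definition of active disease. State whether histologic evidence alone is enough and, if an endoscopic score is used, name it and its cut-off. This review does not say which definition is right.
2. In 7.3, delete *eligible*, so that the primary safety analysis includes all randomised subjects who received at least one dose of study medication, including the antibiotic or its placebo.

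The cost is protocol wording only. Sample size, visits and data collection are unchanged.

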5.1. Schedule of Events

SCREENING		BLINDED TREATMENT							OPEN-LABEL FMT						FO	OLLOW	Early Termination		
	Day	Day			Visit Week (± 2 days)			1	Day			Visit Week (± 2 days)			Month				
Procedures	-90 to -9	-8	-1	0 (Wk 1, D1)	2-3	4	5-7	8		-8	-1	0 (Wk 9, D1)	Weekly	Every 4 weeks	1,	2,4,5	3	EOS 6	
Informed Consent	х																		
Eligibility	х								Ş										
MD visit	х			х		х		х	Į DIL			x		х			х	х	
HBV, HCV, HIV ³	х								UNBLINDING										
Lavage	х								NN										
Colonoscopy (up to 105 days)	х																		
Randomization		x																	
Antibiotics ¹ /placebo		Х								\mathbf{X}^{11}									
hCG ³	х	X ⁸				x		x		X^8				х					
Labs ²	х			х		х		х	1			х		х			х	х	х
Disease activity surveys 5	х	х	х	х	х	х	х	х		х	х	х	x			x	х	х	х
Stool sample ^{7,9}		х		х	х	х	х	х		х		х	x				х	х	х
AE assessment by RN/MD		х	х	х	х	х	х	х		х	х	х	х	х		x ⁶	х	х	х
Telephone contact by RN/MD			x								x					х			
FMT/placebo dosing				X^4	х	х	х	х				X ^{4,10}	X ¹⁰						

¹7-day induction regimen of 3 antibiotics (vancomycin 125 mg, polymixin 62.5 mg, and metronidazole) BSA for vancomycin 125 mg, polymixin 62.5 mg = SQRT [(cm*kg)/3600]

<0.5 m²: PO 1 capsule, TID

 $0.5 - 1 \text{ m}^2$: PO 2 capsules, TID

1-1.5 m²: PO 3 capsules, TID

1.5 -2 m²: PO 4 capsules, TID

Metronidazole weight-based dosing parameters

12.5 kg \geq Patient Weight > 25.0 kg: 125 mg PO BID 25.0 kg \geq Patient Weight > 37.5 kg: 250 mg PO BID 37.5 kg \geq Patient Weight > 50.0 kg: 375 mg PO BID Patient Weight \geq 50 kg: 500 mg PO BID

² "Screening labs" are considered for research purposes only, and will be covered by the study. Routine laboratory assessments are per routine clinical care, and if you are a patient at BCH, these will be

covered by the subject's insurance company. If the patient is not seen at BCH, then these are considered for research purposes and will be covered by the study.

³ HBV, HCV, HIV, and hCG testing are research-only labs and are required to be obtained no earlier than 2 weeks prior to the 1st FMT dose.

⁴ Initial FMT/placebo dose (Week 1 of blinded therapy will be administered as a retention enema). Week 1 of open label therapy will be a selective FMT induction enema or FMT weekly capsule.

⁵ Disease activity surveys include the Patient Reported Outcomes Diary and Pediatric Ulcerative Colitis Activity Index

⁶ Weekly telephone AE Assessments will also be conducted on a weekly basis for the 1st month of follow-up.

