⁷ IBD Biomarkers (quantitative fecal calprotectin) will be done after study completion from frozen samples taken from every study stool sample.

⁸ A urine pregnancy test should only be obtained on day -8 if one has not been done in the past 30 days.

⁹ The "X" location of stool samples indicates when the stool will be collected from the participant. I.e. stool will be collected from the subject on day -8 and Week 1, Day1 however collection kits will

have been provided to the subject beforehand. Lack of stool sample collection will not constitute a protocol deviation.

¹⁰Subjects in the OL treatment will receive FMT (not placebo)

¹¹ If eligible, subjects in OL treatment will receive selective Antibiotics (no placebo).

¹² If a subject received at least 1 dose of FMP IP.

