5.2.2. Fecal microbiota or placebo transplantation (8 weeks)

Approximately 48 hours after stopping antibiotics or placebo antibiotics, subjects will return for a clinic visit in the Clinical and Translational Study Unit (CTSU) for administration of either FMT or placebo. At the visit, they will undergo a medical exam by the investigator and laboratory samples will be collected. Subjects will then receive an induction retention enema of either FMT or placebo over a 15-30 minute period and will be encouraged to retain the inoculum for as long as possible. Subjects will be observed for 60 minutes after last enema and before discharge.

Subjects will return to the CTSU weekly, for a total of 7 weeks, for administration of blinded study treatment (FMT from the same donor or placebo). Prior to each weekly visit, subjects will provide stool and complete a survey (PUCAI) to monitor symptoms, medications and disease activity. At week 4 and week 8, subjects will also have routine laboratory assessments and a medical examination by the investigator. Adverse events will be assessed at each visit.

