5.2.3. Open-label FMT or Follow-up

After completing 8 weeks of blinded study treatment, study subjects will be given the option to receive open-label maintenance FMT weekly for the remainder of the study if they initially received placebo and did not improve OR if they received FMT, improved, and wish to continue treatment. Subjects will be considered to have improved if their PUCAI score shows improvement of at least 10 points compared to baseline or a score of 10 points or less.

After a subject receives the last dose of blinded study treatment at week 8, the subject's treatment assignment will be unblinded to determine the appropriate course of action. Those subjects, who 1) are found to have improved after receiving 8 weeks of placebo or 2) are found not to have improved after receiving 8 weeks of FMT, will not be eligible to receive open-label FMT. Those subjects will be considered in follow up and will have disease status assessments conducted weekly for the 1st month and then monthly for the following month or 5 months. Subjects will also collect a stool sample and have medical examinations done at 3 and 6 months after their last dose of FMT.

Study subjects who are eligible and interested in continuing on to open-label FMT can be enrolled within 14 days (\pm 7 days) following blinded treatment completion. For the open label phase, subjects who received active treatment (FMT) will proceed directly to open label treatment weekly capsules. However, subjects randomized to placebo (aka no antibiotics, no FMT) will undergo a 7-day antibiotic conditioning and a 2-day rest period prior to commencing open-label FMT treatment that will begin with a retention enema. Thereafter, all subjects will return weekly for observed FMT administration as previously described, AE assessment and survey and stool collection. Routine laboratory assessments and medical exams will be conducted monthly. At all times during this study, standard of care progression of medical/surgical therapy will be offered if clinical course dictates it is necessary for both FMT and placebo arms of the study.

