5.2.5. End of Study or Early Termination Visit

If withdrawing early from the study for any reason, subjects will be invited to come in for a final visit to provide a stool sample and routine labs (if indicated).

Follow-up for subjects who signed the consent form, but did not complete the study (**does not include screen failures**) is as followed:

- Active (full follow-up schedule) if subject received at least one dose of FMP IP.
- Active-abbreviated (Subjects will be called weekly for one month and then once at the second month for a total of two months), for subjects that received at least one dose of antibiotics and/or placebo IP but did not complete blinded treatment period or receive any FMP.

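### The blinded arms differ in antibiotic conditioning as well as FMT, but sections 2.1, 7.1 and 7.3 attribute the between-arm result to FMT

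*Combined protocol and SAP*

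**What the plan says.** Section 5.2.1 places conditioning after randomisation: "subjects will receive an induction antibiotic regimen (or corresponding placebo if in placebo arm) for one week". It adds that "Corresponding placebo for each antibiotic will be supplied and distributed by the BCH Research Pharmacy". Section 5.2.3 confirms what the control arm is when it describes "subjects randomized to placebo (aka no antibiotics, no FMT".

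Section 1.2 shows that conditioning is deliberate: depleting the resident flora is expected to help the transplant take hold. The same section cites a retrospective cohort in which 7 of 15 patients reached remission on antibiotics alone.

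The aim and analysis are worded differently:

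- Section 2.1 sets the aim as judging how safe and tolerable universal-donor FMT is against placebo.
- Section 7.1 asks whether FMT is safe and compares a placebo proportion with an FMT-group proportion. It counts new SAEs or worsened AEs after enrolment, whatever their cause.
- Section 7.3 includes anyone eligible and randomised who took at least one dose, and counts first-week antibiotics or their placebo as study medication. It describes the result as the safety of FMT and the biomarker model as an association with FMT.
- Section 5.3.3 defines its safety outcome by FMT-related events of grade 2 or above, with the proportion taken at 8 weeks post-FMT.

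Section 5.2.5 provides a follow-up schedule for subjects who "received at least one dose of antibiotics and/or placebo IP but did not complete blinded treatment period or receive any FMP".

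**The concern.** The arms differ in two active components and the stated conclusion names one. A between-arm difference in all-cause safety, remission, biomarkers or overall microbial composition would be evidence about antibiotics followed by FMT. It would not show which component was responsible. A finding of equivalence has the same limit: it would describe the regimen, and an effect of one component could offset an effect of the other.

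The presence of donor organisms in recipients is an exception, because antibiotics cannot supply them. How well they engraft may still depend on conditioning, as section 1.2 expects.

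At stake is what a paediatric safety trial can say about the product it tests. The test itself is not in doubt.

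**Working it through.** **1. What each arm receives in the blinded phase (5.2.1, 5.2.2, 5.2.3).**

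| Arm | Conditioning week | Then, 8 weekly doses |
|---|---|---|
| FMT | three antibiotics | FMT enema, then capsules |
| Placebo | placebo antibiotics | placebo enema, then capsules |

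No arm has antibiotics with placebo FMT, or FMT without antibiotics. The open-label phase does not separate them either: former placebo subjects are conditioned before FMT, and FMT-arm subjects have already been conditioned.

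**2. Who and what enters the 7.1/7.3 proportion.** The count starts at enrolment and the analysis set starts at one antibiotic or placebo dose. Two consequences follow:

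- An event in the conditioning week of an FMT-arm subject counts in the FMT-group numerator before any FMT has been given.
- An FMT-arm subject who takes antibiotics but never FMT stays in the FMT-group denominator, and in the numerator if an event occurs. Section 5.2.5 foresees such subjects.

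Section 7.3 does mention antibiotics/placebo, but only to define this set.

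**3. Whether the same holds for 5.3.3.** It does not. An event before the first FMT dose cannot be FMT-related, and the 8-week time point is anchored to FMT. The weakness there is attribution after FMT has begun. Section 6.1 speaks variously of relationship to FMT, to study treatment and to FMT/study intervention. Section 3.1 uses study treatment to mean FMT or placebo, while 7.3 counts antibiotics as study medication. An antibiotic-related event has no category of its own.

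**4. The plan's power figure.** Section 7.1 gives 82% with 30 per arm, a 10% rate and a margin of 0.20. One one-sided 0.05 test gives SE = √(2 × 0.10 × 0.90 / 30) = 0.0775 and z = 0.20 / 0.0775 − 1.645 = 0.937, so power is 82.6%, in line with the stated figure. None of these inputs depends on what the active arm is called, so naming the regimen changes neither N nor the test.

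**5. Scale.** One subject is 1/30 = 3.3 percentage points of an arm's proportion. The assumed 10% placebo rate is 3 subjects, and the 0.20 margin is 0.20 × 30 = 6 subjects. This shows how much each misattributed event weighs. It does not say how many to expect, because the documents give no antibiotic AE rate.

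**6. The one antibiotic result cited (1.2).** 7/15 = 47%, exact 95% interval 21% to 73%. This is remission, in a retrospective cohort with refractory acute severe colitis. It makes an effect on disease activity plausible and says nothing about AE rates here.

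**7. Data already scheduled.** Section 5.2.1 says that "stool samples will be collected at the time of study entry and after completion of the antibiotic regimen", and a footnote to the 5.1 schedule says that "stool will be collected from the subject on day -8 and Week 1, Day1". Surveys fall on Day -8, Day -1 and Day 0; "Disease activity surveys include the Patient Reported Outcomes Diary and Pediatric Ulcerative Colitis Activity Index". AE assessments fall on the same three days, and 6.1 records start dates for reported AEs. On Day 0, "laboratory samples will be collected. Subjects will then receive an induction retention enema", so those samples precede FMT. The order is not stated for the Day 0 survey and stool sample.

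**The case against.** The strongest reply is that nothing is hidden. The regimen is set out in 1.2, 5.1, 5.2.1 and 5.2.3, 7.3 openly counts the antibiotic dose, and naming a regimen by its main component is common shorthand. That the result would be published as an FMT result is an inference from the planned wording. This is fair, and it limits the point to wording and reporting. It does not remove it: the objective, hypothesis and analysis text all name FMT, and the analysis set in 7.3 begins before FMT does.

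Three stronger readings are tempting, and the documents do not support them.

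- A reader might infer that every primary safety outcome absorbs antibiotic-week events. Section 5.3.3 does not, and rewording its FMT-related definition could change a primary endpoint.
- A reader might size the problem by time at risk: Day -8 to Day 0 is 8 days, and Day 0 to the Week 8 visit is 7 × 7 = 49, so 8/57 = 14%. But 7.1 gives no end date for counting. If six months of follow-up (about 183 days) counted, the share would be 8/240, about 3%. Neither figure measures the share of events.
- A reader might model how an antibiotic effect would shift the chance of declaring equivalence. Any such shift must be assumed, and the resulting answer would still be correct for the regimen. It would not measure a labelling error.

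**Conclusion.** The point holds as a mismatch between what is randomised and what is concluded. The comparison supports statements about antibiotic conditioning plus FMT against double placebo. As worded, 2.1, 7.1 and 7.3 attribute it to FMT, and the all-cause endpoint includes pre-FMT events and subjects never given FMT. This rests on the text alone and needs no assumed rate.

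The numerical effect cannot be stated, because no document figure sizes antibiotic-related AEs in this population. A reader might go further and infer that the trial is confounded or invalid. That is not supported: conditioning is part of the randomised assignment, is matched with placebo and is intended. The plan should be corrected, because the change is cheap and alters what may be concluded.

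**What to change.** 1. In 2.1, 7.1 and 7.3, state the between-arm contrast and its conclusions as *antibiotic conditioning plus FMT versus double placebo*. Keep the current analysis set and test. Report how many FMT-arm subjects never received FMT. Leave the FMT-related definition in 5.3.3 unchanged.
2. Tabulate AEs by onset: Day -8 to before the first FMT/placebo dose, and from that dose to Week 8. Use the start dates already recorded. Label the second table descriptive, because antibiotic effects can carry over.
3. Record relatedness to antibiotics separately from relatedness to FMT.

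Optional: report the descriptive between-arm change in PUCAI from Day -8 to Day -1 or Day 0, and in stool measures from Day -8 to Day 0, with the number of paired samples. Confirm first that Day 0 collection precedes the enema; the Day -1 survey avoids that question. This is an early antibiotic-versus-placebo contrast. Subtracting it from Week 8 would not isolate the FMT effect.

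The cost is a narrower claim, one extra field and a few tables. No visit is added. Stool pairs may be incomplete, since 5.1 does not treat a missed sample as a deviation. Whether sections 6.1 and 8 agree on which AEs are recorded is a separate matter. Whether both arms should receive the same conditioning is for the sponsor.
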